8. OUTCOME MEASURES

Primary Measure

Low back Pain – This will be measured with a Numeric pain score form $(0-10)^{19,20,21}$.

Secondary Measures

Pain Related Disability - Roland Morris low back pain disability score (RDQ) ^{18,22}. The RDQ and ODI scores are highly correlated, with similar test–retest reliability and internal consistency²³. Good internal consistency is reported for the RDQ, with Cronbach's alpha ranging from 0.84–0.96²².

The primary and secondary measure will be handed and collected on the initial presentation by a non-participating clinician (nurse on duty), it will be handed over in a sealed coded envelope to the principal investigator. The associated investigators

([name] and [name]) performing the initial intervention will be blinded towards these scores.

Re-presentation to the emergency department (ED)

Re-presentation to ED and any medical/allied health input sought by the patient during the next two weeks (asked over the telephone by the follow-up Physiotherapist) will also be recorded and analysed.

The clinician (Physiotherapist – [name]) making the two week telephonic follow-up will be blinded towards the group status and the initial presentation details of the patient.

All scoring sheets will be handed to the principal researcher in a sealed coded envelope to be opened for data analysis.

Adherence to the prescribed exercise program will be recorded on a two week checklist (copy attached), exercise diagrams will be provided to both groups (copy attached). Patients will be advised on the number of repetitions and daily frequency which will be recorded by the patient on the two week checklist provided. The checklist will be returned to the principal investigator by a reply paid envelope (funded by the principal researcher)

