The McKenzie approach unlike other therapeutic methods aims to make the patient as independent of the therapist as possible⁷, thus preventing representations to ED. The McKenzie method of treatment has shown better results than other physical therapy procedures in some acute, sub-acute and chronic low back pain presentations^{5,6}. In particular a high-quality randomised trial in which treatment was based on this approach showed larger reductions in pain²⁷ and disability²⁶ and promoted faster return to work in patients with acute LBP than other conservative therapy recommended by the clinical guidelines¹³. We propose that the 'McKenzie exercise' approach may be a more effective 'additional physiotherapy' intervention for patients seen by physiotherapists in the ED setting then the more standardly used muscular 'stability/mobility exercise' training.

Therefore the purpose of this study is to compare if more benefits are gained with a 'McKenzie exercise' approach compared to a 'stability/mobility' exercise approach for patients who are treated by a Physiotherapist for low back pain in ED. We anticipate the findings of the study will be informative to the best approach to

management of these patients in ED, and may be informative to guide appropriate professional development for physiotherapists who work in ED.

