5. STUDY AIM AND HYPOTHESIS

AIM: To compare the additive clinical benefits (pain, disability, re-admission) of a McKenzie exercise approach (Mechanical Diagnosis and Therapy) versus a stability/mobility exercise approach, to that of usual care for patients who are managed by physiotherapists for their low back pain to ED, both in the immediate (immediately following intervention within ED), and short-term (2 weeks following ED consultation) time points.

Hypothesis: A McKenzie exercise approach (Mechanical Diagnosis and Therapy) will have greater additional benefits (pain, disability, re-admission) for patients who present with low back pain to ED than will a stability/mobility exercise approach, both in the immediate (immediately following intervention within ED), and short-term (2 weeks following ED consultation) time period.

Null Hypothesis: The McKenzie exercise approach will have no beneficial effects compared to the stability/mobility exercise approach for patients who present with low back pain to ED either in the immediate (immediately following intervention within ED), and short-term (2 weeks following ED consultation) time period.

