7. PARTICIPANTS

Fifty participants (25 in each exercise group) will participate in the study.

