7.2 EXCLUSION CRITERIA

History of substance abuse eg: IV drug user (IVDU), ETOH Spinal fractures.

Pregnant women

Neurological compromise (as shown by loss of strength, sensations and reflexes).

Red flags eg: loss of weight, fever, history of cancer.

Multiple medical co-morbidities (chronic obstructive pulmonary disease, ischemic heart disease, chronic kidney disease, uncontrolled diabetes and hypertension).

Patients brought in by police who are under influence of illicit drugs and alcohol.

Patients bought in by police who will remain in custody.

Patients with known cognitive and intellectual disability (decided on the basis of information collected by the triage nurse).

Patients having an acute concurrent systemic illness.

Patients with congenital spinal structural deformity.

Patients unable to provide consent and comply with the home exercise program.

Sample size was calculated on the primary outcome measure Numeric pain score . To calculate a sample size between two independent means for a two tailed test at a significance of less than 0.05, a power of ≥ 0.8 for the outcome measure (pain score) a conservative minimum clinically important difference of 2 (± 2.5) was used^{19,20, 21}. This predicted that 25 patients in each group would be required.

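### The two-week health-care-use outcome is not limited to low back pain, and no reason for contact is listed for collection, so unrelated contacts would pull the comparison towards no difference (minor).

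*Protocol*

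**What the plan says.** Protocol section 8 lists, under its sub-heading on return to the emergency department (ED), "Re-presentation to ED and any medical/allied health input sought by the patient during the next two weeks". The source is a telephone call at two weeks: "asked over the telephone by the follow-up Physiotherapist) will also be recorded and analysed". Neither the ED element nor the wider health-care element is restricted to the back. Sections 8 and 10 between them describe the call as covering the pain score, the Roland Morris score and these contacts; a reason for contact is not mentioned.

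The purpose of the outcome is specific to the back. Section 4 says that delayed treatment of back pain sometimes brings patients back to ED, and that the McKenzie approach makes patients more independent of the therapist, "thus preventing representations to ED". Section 5 hypothesises "greater additional benefits (pain, disability, re-admission) for patients who present with low back pain to ED". Re-admission is not defined there; the ED-return outcome in section 8 is the closest match.

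Two further provisions bear on the point. Section 9 gives every patient a GP letter that includes a physiotherapy follow-up plan, and section 10 offers every patient physiotherapy two weeks after discharge. Section 11 names tests for pain, disability and short-stay admission, but none for this outcome.

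**The concern.** Neither exercise programme can prevent a visit for a cold, a dental problem or an injury, yet the wording of section 8 would include each of them. Such contacts do not cancel because they are equally common in both arms. They raise both proportions, narrow the gap between them and add variance. A real reduction in back-pain returns could be hidden, and a chance imbalance in unrelated visits could be read as an exercise effect.

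This differs from a detail that a later analysis plan can settle. The reason for a contact has to be asked on the call. If it is not asked, no later definition can recover it from the items the protocol describes.

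**Working it through.** **Inputs from the protocol.** "Fifty participants (25 in each exercise group) will participate in the study" (section 7). "Sample size was calculated on the primary outcome measure Numeric pain score" (section 7.2), "for a two tailed test at a significance of less than 0.05", with power of at least 0.8, difference 2 and SD 2.5.

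**The plan's own figure.** n per arm = 2(1.96 + 0.8416)² × 2.5² / 2² = 24.5, so 25. The stated size reproduces by the normal approximation (an exact t-test calculation gives 25.5, so 26). It is not in dispute here. It concerns pain only, and no calculation supports the health-care-use outcome.

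**Dilution.** Let p₁ and p₂ be the proportions with a back-related contact in the stability/mobility and McKenzie arms. Let u be the proportion in each arm with an unrelated contact, independent of arm and of back-related contacts. The proportion with any contact is then

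P = 1 − (1 − p)(1 − u),

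so P₁ − P₂ = (p₁ − p₂)(1 − u). The difference shrinks by exactly (1 − u), and P₂/P₁ moves towards 1.

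**Size, on assumed rates.** The protocol gives no contact rates; every p and u below is an assumption. Power is by exact enumeration of the uncorrected 2×2 chi-square test, 25 per arm, two-sided 0.05.

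| Back-related rates | u | Observed rates | Difference | Risk ratio | Power |
|---|---|---|---|---|---|
| 25% vs 12.5% | 0 | 25.0% vs 12.5% | 12.5 points | 0.50 | 0.21 |
| | 2% | 26.5% vs 14.3% | 12.3 | 0.54 | 0.20 |
| | 5% | 28.8% vs 16.9% | 11.9 | 0.59 | 0.18 |
| | 10% | 32.5% vs 21.3% | 11.3 | 0.65 | 0.15 |
| | 20% | 40.0% vs 30.0% | 10.0 | 0.75 | 0.13 |
| 40% vs 10% | 0 | 40% vs 10% | 30.0 points | 0.25 | 0.73 |
| | 5% | 43.0% vs 14.5% | 28.5 | 0.34 | 0.64 |
| | 10% | 46% vs 19% | 27.0 | 0.41 | 0.56 |
| | 20% | 52% vs 28% | 24.0 | 0.54 | 0.45 |
| | 30% | 58% vs 37% | 21.0 | 0.64 | 0.36 |

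Worked line: for 25% vs 12.5% and u = 20%, P₁ = 1 − 0.75 × 0.80 = 0.40 and P₂ = 1 − 0.875 × 0.80 = 0.30. The difference is 0.10 = 0.125 × 0.80.

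The first block halves the rate; the second assumes a fourfold reduction, which is large for two active exercise arms. The table treats the outcome as one yes/no variable, which the protocol does not specify. The same formula applies to each element taken separately, with its own p and u.

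**The case against.** - **All-cause counting is inferred.** The protocol does not say that contacts count whatever their cause. Its wording may range over types of provider, and in a back-pain trial the caller may well ask about this episode. This stands: a reader might infer a deliberate all-cause rule, and the text does not go that far. It does leave the restriction unstated, so following it literally includes unrelated contacts.
- **The reason may be recorded.** A reader might conclude that the two kinds of contact can never be separated. The call script is not in the protocol, so that cannot be concluded. What can be said is that the reason is not among the items described.
- **A single composite is not stated.** If ED return is analysed alone, unrelated GP visits do not affect it; only unrelated ED visits do. This stands too.
- **The loss may be negligible.** Patients are aged 20 to 50, major co-morbidity and acute systemic illness are excluded, and follow-up is two weeks. At u = 2% and halved rates, power moves only from 0.21 to 0.20. With effects of that order the comparison is uninformative with or without a fix. Nor does section 11 name a test for this outcome, which may be meant descriptively. The argument from power is therefore weak; the blurred meaning of the estimate remains.
- **Restricting to back pain is not enough.** The GP letter and the offered physiotherapy produce back-related contacts in both arms, and an outcome of all care for low back pain would still count them. This is correct, and the fix allows for it.
- **All-cause use is a legitimate measure** and avoids attribution by the patient. That is a reason to keep it alongside, not to make it the only measure of a back-specific hypothesis.

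**Conclusion.** The outcome as worded does not match the back-specific benefit it is meant to show. The direction of the effect is certain if unrelated contacts are counted and are equally frequent in both arms: the difference shrinks by (1 − u) and the risk ratio moves towards 1. Its size cannot be taken from the protocol. On the assumptions shown it runs from almost nothing (u = 2%, halved rates) to a loss of about half the power (0.73 to 0.36 at u = 30% with a fourfold effect).

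The priority is minor. This is a secondary outcome, the sample size rests on pain, and the primary result is untouched.

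**What to change.** In section 8, have the caller ask two things about each reported contact: was it for the low back pain, and was it planned follow-up (arising from the GP letter or the offered physiotherapy) or unplanned? State that ED return for low back pain and unplanned care sought for low back pain are analysed as separate outcomes, with planned follow-up and all-cause contacts reported alongside.

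The cost is two short questions per contact in a call already planned, and a sentence or two in section 8. The drawback is that the reason is reported by the patient and may be misattributed; the all-cause count serves as a check. The change makes the estimate interpretable. It does not give 25 per arm adequate power for modest differences in this outcome.

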9. INTERVENTIONS

All patients will receive the standard usual care provided in ED as detailed in section 4 that also includes a letter to their regular general practitioner (GP) outlining the assessment, management, and follow-up physiotherapy plan.

In addition to this standard care patients will also receive one of two additional physiotherapy exercise approaches provided to them during the ED consultation.

9.1 McKenzie Exercise Approach Group

Patients in this group will be assessed and treated using mechanical diagnosis and treatment (McKenzie) concepts. This method involves the assessment of symptomatic and mechanical responses to repeated movements and sustained positions. These responses are used to classify them into subgroups or syndromes (Postural, Dysfunction and Derangement), which help in guiding the treatment principles⁴⁻⁶.

9.2 Standard Exercise Approach Group

Patients in this group will receive standard ED physiotherapy assessment and treatment which includes the commencement of spinal stabilisation exercises¹⁰ and mobility exercises.

10. STUDY PROCEDURE

Participant recruitment and consent process: The patients presenting to the emergency department are triaged by nursing staff, assessed by medical staff/Physiotherapist and accordingly given analgesia. After 30 minutes of receiving analgesia, the patient will be approached by the Physiotherapist and given information regarding the study and if the patient is agreeable, written consent will be obtained.

Baseline outcome measures: The initial pain score (0-10), Roland Morris score will be recorded by the patient themselves without any guidance from the investigator. They will be handed over by a non-participating clinician (nurse on duty).

Group allocation process: Patients will then be randomised to one of the two groups via sealed envelopes (concealed allocation picked by non-participating medical/nursing staff).

Intervention: The participant will then be assessed for lumbar range of motion, neurological status, lumbar stability and mobility. Depending on the group the patient belongs, exercise will be performed under supervision. The participant will be provided with exercise sheets and checklist for home. Participants will be offered follow-up Physiotherapy two weeks after discharge in a public or private setup depending on his/her preference and availability of private cover.

Follow-up outcome measures: The two week telephonic follow-up to record the pain score, Roland Morris disability score will be obtained by a non-participating Physiotherapist. The exercise check-list provided to the patient on discharge, will be returned to the principal investigator by a reply paid envelope funded by the principal investigator. Patients are unaware of the follow-up process and thus will not feel as if they are being offered special treatment to participate in the study.

Resource impact on service: There will be negligible impact of services in ED as both treatment types are presently being used by Physiotherapists in treatment of LBP patients in ED at RBWH. Some of the outcome measures are not routinely done in ED will only take an additional 20-30minutes to complete without any clinician time being utilised. The referral process will not add to the workload to peripheral hospitals as the patient would normally be referred anyway.

11 DATA ANALYSIS

All analysis will be on the basis of an intention to treat analysis. The two groups will have their demographics compared at baseline by a combination of parametric (ttests) and non-parametric (chi-square tests). The data for pain and disability score will

be tested and if found to have a normal distribution will consist of a between/within repeated measures ANOVA to test if there is a difference between groups over time. If a non-normal distribution is found a Kruskal Wallis test will be used. The need for admission to a Short stay unit will be compared between groups by a chi-square crosstabs.

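### The sample size is for two independent means, but pain is to be tested by repeated-measures ANOVA; baseline-adjusted ANCOVA would be more powerful, and whether the ANOVA falls short of 0.8 depends on what the 2.5 refers to

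*Protocol*

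**What the plan says.** The sample size paragraph at the end of Protocol section 7.2 describes its calculation this way: "To calculate a sample size between two independent means for a two tailed test at a significance of less than 0.05". For the effect it says that "a conservative minimum clinically important difference of 2 (± 2.5) was used", and it concludes: "This predicted that 25 patients in each group would be required". Section 7 repeats the total: "Fifty participants (25 in each exercise group) will participate in the study".

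Section 11 names a different test for pain and disability. If the data look normal, it is a "between/within repeated measures ANOVA to test if there is a difference between groups over time"; if not, the analysis switches to a Kruskal Wallis test.

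Section 10 gives the measurements. At baseline, before allocation: "The initial pain score (0-10), Roland Morris score will be recorded by the patient themselves". Afterwards: "The two week telephonic follow-up to record the pain score, Roland Morris disability score will be obtained by a non-participating Physiotherapist". The procedure schedules no other pain score, although the aim in section 5 also names a time point immediately after the intervention.

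The protocol gives no correlation between baseline and follow-up, no SD identified as that of change, and no baseline-adjusted analysis.

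**The concern.** The sample size and the analysis concern the same primary outcome but describe different tests. A comparison of two independent means of the 2-week score has the SD of that score as its noise term. A group-by-time test has the SD of change, which can be larger or smaller depending on how strongly baseline and follow-up correlate. The 25 per group carries over to the planned test only if the 2.5 is the right SD for it, and the protocol does not say so.

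A low correlation cannot be ruled out. Patients are approached 30 minutes after analgesia during an emergency visit, and the follow-up score is taken by telephone two weeks later, after home exercise. What is at stake is power for the 2-point difference that the protocol itself treats as clinically important, when a baseline score that is already collected could be used more efficiently.

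**Working it through.** **Inputs.** From section 7.2: difference 2, ± 2.5, two-sided 0.05, power at least 0.8, 25 per group. From section 10: two pain scores, at baseline and 2 weeks. The correlation ρ between them is not in the protocol, so a range is assumed. No baseline difference between the randomised groups is assumed.

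**1. The plan's own figure.** n per group = 2 × [2.5 × (1.960 + 0.842) / 2]² = 24.5, rounded up to 25. The stated 25 is reproduced. Power at 25 is 0.807 by the normal formula and 0.791 by the exact non-central t, which would ask for 26. The figures below use the exact t, so 0.79 is the benchmark that the plan's own design reaches.

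**2. The planned test.** With two occasions, the group-by-time F equals the square of the t statistic on change scores. With the same score SD at both visits:

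- SD of change = SD of score × √[2(1 − ρ)]
- ANCOVA residual SD = SD of score × √(1 − ρ²)
- non-centrality = 2 / [SD × √(2/25)], with 48 df for change and 47 for ANCOVA

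**3. If 2.5 is the SD of a single score:**

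| ρ (assumed) | SD of change | Power, group-by-time | ANCOVA residual SD | Power, ANCOVA |
|---|---|---|---|---|
| 0 | 3.54 | 0.50 | 2.50 | 0.79 |
| 0.2 | 3.16 | 0.59 | 2.45 | 0.81 |
| 0.3 | 2.96 | 0.65 | 2.38 | 0.83 |
| 0.4 | 2.74 | 0.72 | 2.29 | 0.86 |
| 0.5 | 2.50 | 0.79 | 2.17 | 0.89 |
| 0.6 | 2.24 | 0.87 | 2.00 | 0.93 |

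The group-by-time test crosses 0.80 at ρ = 0.49 (normal) or 0.51 (exact t). ANCOVA crosses it at about 0.15 by exact t and is 0.79 near zero. By the normal formula the group-by-time test would need 35 per group at ρ = 0.3 and 30 at ρ = 0.4.

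**4. If 2.5 is the SD of change.** The group-by-time test is then the very comparison that was sized: 0.807 (normal) or 0.791 (exact t), whatever ρ is. The score SD becomes 2.5 / √[2(1 − ρ)], so the ANCOVA residual SD is 2.5 × √[(1 + ρ)/2]. At ρ = 0.2 this is 1.94 (power 0.95), at 0.5 it is 2.17 (0.89), and at 0.7 it is 2.30 (0.85).

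**5. If the SDs differ between visits.** The SD of change exceeds the follow-up SD only when ρ is below (baseline SD) / (2 × follow-up SD). With an assumed baseline SD of 1.5 and a follow-up SD of 2.5, that is 1.5 / 5 = 0.3. The value of 0.5 therefore belongs to the equal-SD case.

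**The case against.** The strongest objection is that the shortfall rests on an undefined figure. Section 7.2 attaches the 2.5 to a minimum clinically important difference, and the titles of the three references cited there (19 to 21) all speak of changes or change scores. Titles do not settle the matter, but they make an SD of change a real possibility. On that reading the sizing and the analysis agree. This stands, and it means that the protocol does not support what a reader might infer from the mismatch alone, namely that the trial misses its stated power. That follows only if 2.5 is a single-score SD, the SDs are similar at both visits and the correlation is below about 0.5.

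Three further inferences are also unsupported:

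- **Group main effect.** It would have low power because it averages in the pre-treatment score. But section 11 speaks of a group difference over time, which most naturally means the interaction.
- **Dropout.** Repeated-measures ANOVA loses patients without a 2-week score, but ANCOVA of the 2-week score loses the same patients, so this does not separate the two.
- **ANCOVA always reaches 0.8.** By exact t it is 0.79 at correlations near zero. That small gap comes from rounding the sample size by the normal formula.

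It is also fair to say that the planned test is valid under randomisation, so this is a matter of efficiency and not of bias. What survives is that ANCOVA was the more powerful test in every scenario computed under either reading of the 2.5, and that the protocol does not connect its sample size to its analysis.

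**Conclusion.** The point holds as a should-fix. If 2.5 is the SD of single scores, equal at both visits, the planned group-by-time test has power 0.59 to 0.79 for correlations of 0.2 to 0.5, against 0.81 to 0.89 for ANCOVA: a loss of about 0.22 at the low end and 0.10 at the high end. If 2.5 is the SD of change, there is no shortfall against the target, but ANCOVA would still raise power from 0.79 to between 0.85 and 0.95 for correlations of 0.7 down to 0.2.

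These results assume 25 analysed per group, no baseline difference, two pain scores and a correlation that the protocol does not give. The 25 per group is correct for its own inputs; the fault lies in the missing link between it and section 11.

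**What to change.** In section 11, replace both the repeated-measures ANOVA and the normality-triggered switch to Kruskal Wallis with wording such as: *The primary analysis is ANCOVA of the 2-week pain score on group and baseline pain score, reporting the adjusted mean difference with 95% CI. RDQ is analysed the same way.* Keep any rank-based test as a sensitivity analysis only; if the switch stays, the gain from adjustment is not secured.

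In the sample size paragraph of section 7.2, state that the calculation refers to the 2-week score and whether 2.5 is the SD of scores or of change.

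If an immediate post-intervention score is to be collected, as the aim in section 5 implies, use a baseline-adjusted linear mixed model with a group-by-visit term and name the primary time point. Naming 2 weeks as primary is a design decision that the sponsor should make explicitly, because the protocol currently names none.

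The cost is a change of wording and one degree of freedom. For the 2-week analysis no extra patients, visits or data are needed.

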12 WITHDRAWAL FROM STUDY PARTICIPATION

In accordance with the Declaration of Helsinki, each subject has the right to withdraw from the study at any time. An investigator also has the right to withdraw subjects from the study in case of any adverse effect, lack of compliance or reasons concerning the subject's wellbeing.

In case of withdrawal, the subject will continue to receive standard care in ED and follow-up as appropriate. Clinical notes will be documented for the same

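### The repeated-measures ANOVA in section 11 amounts to an unadjusted comparison of change scores; a baseline-adjusted comparison is more precise and better protected against baseline-related loss

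*Protocol*

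**What the plan says.** Section 11 of the Protocol sets the principle: "All analysis will be on the basis of an intention to treat analysis". For pain and disability it then names, if the data are normally distributed, a "between/within repeated measures ANOVA to test if there is a difference between groups over time". Otherwise: "If a non-normal distribution is found a Kruskal Wallis test will be used". It does not define intention to treat and does not mention adjustment for the baseline score.

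The primary outcome is the 0-10 pain score (section 8). Section 10 has it recorded in the ED before randomisation and once more afterwards: "The two week telephonic follow-up to record the pain score, Roland Morris disability score will be obtained by a non-participating Physiotherapist". The same section adds that "Patients are unaware of the follow-up process".

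Section 12 lets participants leave ("each subject has the right to withdraw from the study at any time") and lets the investigator remove them: "An investigator also has the right to withdraw subjects from the study in case of any adverse effect, lack of compliance". It does not say whether outcome scores are still sought after withdrawal.

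The sample-size paragraph at the end of section 7.2 uses a difference of 2 (± 2.5), two-sided 0.05 and power of at least 0.8. It arrives at 25 per group, which is also the number to be recruited (section 7).

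**The concern.** With one baseline and one follow-up score, the group-by-time test of this ANOVA is the same test as a two-sample t-test on change. Two things follow.

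First, the method takes the full baseline difference off the two-week score, whatever the correlation between the two. If that correlation is modest, this adds noise, and it carries any baseline imbalance among the analysed participants into the estimate.

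Second, a participant with only a baseline score contributes nothing to the test. Some missing scores are foreseeable: follow-up is one telephone call that patients do not expect, and withdrawal is allowed for reasons, such as an adverse effect or poor compliance, that need not be random or equal between two exercise programmes. If those lost differ in baseline pain between the arms, the completers are no longer balanced at baseline, and the change contrast picks up that imbalance.

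At stake are the power of a 50-patient trial sized with no allowance for loss, and a modest bias that data already collected could remove.

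**Working it through.** **Inputs from the Protocol.** Difference 2; SD 2.5 (the ± figure read as the SD); two-sided 0.05; 25 per arm; scores at baseline and two weeks.

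**Assumptions, because the Protocol gives no figure.** Baseline/two-week correlation r of 0.2, 0.3 or 0.5; equal SD at both times; the loss patterns stated below.

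**1. The plan's own figure.** n per arm = 2 × [2.5 × (1.960 + 0.842) / 2]² = 24.5, so 25. The exact t-test gives 25.5, so 26; power at 25 per arm is 0.807 (normal approximation) or 0.791 (t-test). The stated 25 is reproduced. The calculation compares two independent means with SD 2.5, which matches a comparison of change only if the SD of change is also 2.5, that is, if r = 0.5.

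**2. Precision with complete data.** SD of change = 2.5 × √(2(1 − r)). Residual SD after baseline adjustment = 2.5 × √(1 − r²). T-test power for a difference of 2 with 25 per arm:

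| r | SD of change | Power, change | Adjusted SD | Power, adjusted |
|---|---|---|---|---|
| 0.2 | 3.16 | 0.59 | 2.45 | 0.81 |
| 0.3 | 2.96 | 0.65 | 2.38 | 0.83 |
| 0.5 | 2.50 | 0.79 | 2.17 | 0.89 |

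The variance ratio, change to adjusted, is 2/(1 + r): 1.67, 1.54 and 1.33. (The adjusted power ignores the one degree of freedom spent on the baseline term.)

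**3. Bias from baseline-related loss, no true effect.** Suppose one arm loses 30% of those above mean baseline pain and 10% of those below, and the other arm the reverse. Overall loss is 20% in each arm.

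- Mean distance from the centre within each half: 2.5 × √(2/π) = 1.99.
- Completers' baseline shift in the first arm: (0.35 − 0.45)/0.80 × 1.99 = −0.25. The other arm: +0.25. Difference between arms: 0.50.
- The two-week means differ by r × 0.50, so the change contrast is off by 0.50 × (1 − r): 0.40, 0.35 and 0.25 for r = 0.2, 0.3 and 0.5. That is 20%, 17% and 12% of the 2-point target.
- If only one arm has this pattern and the other loses 20% at random: 0.25 × (1 − r) = 0.20, 0.17 and 0.12.
- If both arms have the same pattern, or loss is random: about 0.

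In a large simulation of the mirror-image pattern, a baseline-adjusted estimate on the same completers was off by 0.02 or less.

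**4. Effect on false positives.** Simulating 20,000 trials of 25 per arm for each case, the nominal 5% error of the change contrast was 6.7%, 6.6% and 6.2% (r = 0.2, 0.3, 0.5) for the mirror-image pattern, 5.3% to 5.7% with one arm affected, and about 5% with the same pattern in both arms.

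**5. Loss that depends on the unseen two-week score.** With such loss in one arm only (about 24% against 20% at random in the other), the bias was 0.36 and 0.25 points for the change contrast at r = 0.3 and 0.5, and 0.47 and 0.39 for the baseline-adjusted estimate. Adjustment does not cure this kind of loss and here does somewhat worse.

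**The case against.** A reader might infer that section 11 contradicts itself: it promises intention to treat, yet the ANOVA makes the primary analysis a completers' analysis. The Protocol does not support that. It does not define intention to treat; read as analysis in the allocated group, the ANOVA satisfies it. The text never restricts the analysis to completers, and an ANOVA can be run on imputed scores. How missing scores are handled is commonly left to a SAP, which may exist, so the lack of a rule here is no finding.

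Nor is deletion what causes the bias in step 3. With one follow-up score, ANCOVA leaves out the same participants and is essentially unbiased there. What differs is whether the comparison conditions on baseline.

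It can also be said that the mirror-image pattern is severe, that the Protocol gives no loss rate, mechanism or correlation, and that even this pattern raises the type I error by less than 2 percentage points. All of that stands. Bias is a possibility, not a prediction.

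One further caveat: sections 5 and 6 also speak of an outcome immediately after the intervention, but section 10 schedules no such measurement. The algebra above rests on the two scores that section 10 lists.

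The precision argument survives all of this. It needs no missing data and concerns a method that the Protocol itself has fixed.

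**Conclusion.** The point holds as a weakness of the chosen method, not as a breach of intention to treat. On the two scores listed in section 10, the named ANOVA is an unadjusted change comparison that by default omits participants without a two-week score. At SD 2.5 and r between 0.2 and 0.5, baseline adjustment raises power by about 0.10 to 0.22 with the same 50 patients; the change contrast falls well short of 0.8 power at r of 0.2 or 0.3. Under assumed baseline-related loss that differs by arm, the change contrast is biased by about 0.12 to 0.40 points against a target of 2, and the adjusted estimate is not. If loss is random or alike in both arms, there is no bias to remove and only the gain in precision remains. If loss depends on the unseen score, neither method is safe.

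**What to change.** In section 11, replace the repeated-measures ANOVA for pain and the RDQ, and the Kruskal-Wallis branch with it, by a comparison of two-week scores between the groups as randomised, adjusted for the baseline score. This can be an ANCOVA or the equivalent mixed model with a common baseline mean. The Kruskal-Wallis branch should go too, since it likewise uses observed scores only and names no baseline adjustment.

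In section 12, state that the two-week score will still be sought from withdrawn participants who agree to give it.

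Add one sensitivity analysis that shifts the missing two-week scores by stated amounts, separately by arm, because adjustment does not deal with loss that depends on the unseen score.

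The cost is a change of wording, slightly more analysis and some calls to withdrawn participants; no new measurement is needed. Neither ANCOVA nor the mixed model recovers much of the power lost to missing scores.
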